### II. AIMS OF THE REGISTRY

### A. Primary Objective:

The primary objective of the Registry is to study all-cause mortality at one, three and five years in a large (approximately 6,000) consecutive and relatively unselected cohort of patients with heart failure and/or with left ventricular dysfunction. The patients will be stratified according to symptoms, etiology of disease, ejection fraction and chest X-ray findings at entry into the Registry.

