### B. Subsidiary Objectives:

The subsidiary objectives of the Registry are:

1. To study cardiovascular mortality at one, three and five years globally and after stratification according to symptoms, etiology of disease, ejection fraction and chest X-ray findings in the above populations.

2. To study morbid events at one year in the above population.

3. To relate other baseline covariates of prognostic importance to subsequent mortality and morbidity in the above population.

4. To characterize in greater detail clinical characteristics, echocardiographic abnormalities, arrhythmia status, functional capacity and neurohumoral levels and to correlate these detailed findings with subsequent mortality and morbidity in a stratified randomly selected sample of 1000 patients from among the patients entering the Registry.

5. To compare baseline characteristics and follow-up events of this relatively unselected population with those of the SOLVD Trials.

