f) Chest X-ray and electrocardiogram. If not available from the preceding 90 days.

VIII. PERIOD OF PATIENT ACCESSION

The timetable for the SOLVD Registry is as follows:

	YEAR 1 December 1, 1987 - November 30, 1988
Dec. 1, 1987 - Dec. 31, 1987	Phase-in month. Major activities include training session for clinic personnel and quality control for substudy procedures.
Jan. 1, 1988 - Sept. 30, 1988	Nine-month recruitment period
Oct. 1, 1988 - Nov. 30, 1988	Two-month phase-down. Major activities include completing data col- lection of recruitment, evaluating continuation of recruitment of rare etiologies and planning for YEAR 2 follow-up activities.
	YEAR 2 December 1, 1988 - November 30, 1989
Mailing of que	estionnaire on vital statistics
	YEAR 3 December 1, 1989 - November 30, 1990
Vital status a	ascertained by the Coordinating Center with national death registries.
ч.	YEAR 5 December 1, 1991 - November 30, 1992
Vital status a	ascertained by the Coordinating Center with national death registries.
As shown in th	he timetable, patients with the more common etiologies will be enrolled

As shown in the timetable, patients with the more common ethologies will be enfolded during a 9-month period. Since only a few patients with the rarer ethologies (e.g., active myocarditis or specific cardiomyopathy) will be identified at each center per year, patients with these underlying diseases will be recruited until June 1991. A flow diagram for the SOLVD Registry is included in appendix A1.

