If the participant is acknowledged to be alive and has not required any hospitalization during the preceding year, no further information will be required at this time beyond completion of the One-Year Follow-up form. If the participant has died, the research nurse will obtain reports of hospitalizations, if any have occurred, and circumstances of death as well as the death certificate, and will forward a Designation of Death form, the Death Certificate Cover Sheet form, and Hospitalization forms (as needed) promptly to the Coordinating Center. If the participant is living but has required one or more hospitalizations during the preceding year, the nurse will obtain reports of the hospitalizations, and will complete the Hospitalization form for each hospitalization. (Copies of these forms are included in appendix B.)

It should be noted that if a participant is registered in the logbook at a participating center and subsequently dies during the same hospitalization, the center is required to seek his/her eligibility for the SOLVD Registry and to complete and submit to the Coordinating Center the Main Registry Baseline form, the Designation of Death form, and the Death Certificate Cover Sheet for this participant.

There will be a time allowance of 60 days for submitting the one-year follow-up forms to the Coordinating Center, i.e., 60 days after the anniversary of enrollment.

The second type of information derived from the follow-up of the Registry participants will be a long-term ascertainment of vital status through the National Death Index (NDI) and corresponding registries in Canada and Belgium. Although several matching criteria are available for searches of the NDI, the three absolutely essential identifiers include the social security number, the date of birth and the full name of the participant. Information on vital status will be sought approximately two years and four years after enrollment of a patient in the Registry. For the United States, this will be done at the SOLVD Coordinating Center. The Canadian centers and the Belgian center will be responsible for collecting these data from their respective Bureaus of Vital Statistics and for submitting them, upon request, to the SOLVD Coordinating Center.

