#### Endpoint Data

The follow-up endpoints will provide two sets of information. The first set will be one-year information on vital and on major non-fatal cardiovascular events, including recurrent and/or new complications requiring hospitalization such as worsening of functional status, myocardial infarction, stroke, pulmonary complications, severe serious arrhythmias, drug toxicity, and cardiac surgery--including cardiac transplantation. The second set of endpoint data will provide long-term ascertainment of vital status, approximately two years and approximately four years after enrollment in the SOLVD Registry.

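### Five-year mortality is part of the primary objective, but the last scheduled death-registry search closes when the nine-month cohort has at most 4.17 to 4.91 years of follow-up.

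*Protocol*

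**What the plan says.** Four parts of the protocol bear on the point.

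- Objectives (Section II). The primary objective is "to study all-cause mortality at one, three and five years in a large (approximately 6,000) consecutive and relatively unselected cohort". Subsidiary objective 1 uses the same horizons: "To study cardiovascular mortality at one, three and five years globally".
- Long-term ascertainment (Section IX). Follow-up Data states: "Information on vital status will be sought approximately two years and four years after enrollment of a patient in the Registry". Endpoint Data says the same again, describing "long-term ascertainment of vital status, approximately two years and approximately four years after enrollment in the SOLVD Registry".
- Timetable (Section VIII). The nine-month recruitment period is "Jan. 1, 1988 - Sept. 30, 1988". The death-registry searches are placed in project Year 3 (1 December 1989 to 30 November 1990) and, as the last entry, "YEAR 5 December 1, 1991 - November 30, 1992". The project years are counted from December 1987. Rare etiologies are recruited until June 1991, although Section VI leaves that extension to a decision after the first nine months.
- Analysis (Section X). The main variable is time from Registry entry to death, analysed with a proportional hazards model. Cause of death is taken from the death certificate.

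**The concern.** The objective and the data collection name different horizons. Two separate parts of Section IX give about two and four years, so this is not an isolated slip. The labels Year 3 and Year 5 in Section VIII look like three and five years of follow-up, but they are calendar years of the project. A patient enrolled in 1988 is still in the fifth year of follow-up when project Year 5 ends.

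At stake is one stated horizon of the primary objective and of subsidiary objective 1. If no registry search covers a patient's fifth anniversary, five-year mortality for that patient is not observed. No later analysis plan can supply it from the scheduled data.

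**Working it through.** **Inputs.** Main-cohort enrollment runs from 1 January to 30 September 1988 (Section VIII). The search windows are 1 December 1989 to 30 November 1990 and 1 December 1991 to 30 November 1992 (Section VIII). Rare-etiology recruitment runs until June 1991 (Section VIII). The time origin is the date of the qualifying measurement (Section IX, Baseline Data Collection).

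**Formula.** Follow-up in years = (search date − enrollment date) / 365.25.

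| Search date | Enrolled 1 Jan 1988 | Enrolled 30 Sept 1988 |
|---|---|---|
| Year 3 opens, 1 Dec 1989 | 700 days = 1.92 | 427 days = 1.17 |
| Year 3 closes, 30 Nov 1990 | 1,064 days = 2.91 | 791 days = 2.17 |
| Year 5 opens, 1 Dec 1991 | 1,430 days = 3.92 | 1,157 days = 3.17 |
| Year 5 closes, 30 Nov 1992 | 1,795 days = 4.91 | 1,522 days = 4.17 |

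**Step 1: the plan's own figure.** The windows give 1.17 to 2.91 years and 3.17 to 4.91 years. That agrees with Section IX's two and four years. Sections VIII and IX are therefore consistent with each other, and the objective is the part that does not fit.

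**Step 2: five years.** Fifth anniversaries run from 1 January 1993 to 30 September 1993. The timetable closes on 30 November 1992. It falls short by 32 days for the first enrollee and by 304 days (about 10 months) for the last.

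**Step 3: three years.** The last third anniversary is 30 September 1991. The first search closes too early for it. The second opens on 1 December 1991, when every main-cohort patient has at least 3.17 years. Because the analysis uses dates of death, that search yields three-year mortality for the whole main cohort.

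**Step 4: Table 1.** The protocol gives no three-year rates, so I assume a constant annual risk: q = 1 − (1 − p)³. Power is Φ[(|q1 − q2| − 1.96·SE0)/SE1], where SE0 is the pooled and SE1 the unpooled standard error. For Case 9 (n = 120, m = 60, p = .12 and .24):

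- q1 = 1 − .88³ = .319 and q2 = 1 − .76³ = .561
- SE0 = .0774 and SE1 = .0769
- power = Φ[(.2425 − .1518)/.0769] = Φ(1.18) = .88, against .87 printed

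All eleven three-year entries reproduce to within about one point in the same way. The column describes three full years of mortality, which Step 3 shows will be available.

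**Step 5: rare etiologies.** A patient enrolled on 30 June 1991 has 519 days = 1.42 years on 30 November 1992; one enrolled on 1 June 1991 has 548 days = 1.50 years. Anyone enrolled after 30 November 1989 falls short of three years. Five years for a June 1991 enrollee would need deaths through June 1996, about 43 months after the timetable ends.

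**Step 6: what the fifth year holds (illustration).** Assume a constant annual mortality p. Deaths in year five, as a share of the cohort, are (1 − p)⁴ − (1 − p)⁵. Table 1's first-subgroup rates run from .05 to .20:

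- p = .05: .815 − .774 = .041
- p = .12: .600 − .528 = .072
- p = .20: .410 − .328 = .082

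Four-year mortality would therefore lie some 4 to 8 percentage points below five-year mortality. The two horizons are not interchangeable.

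**The case against.** The strongest case on the other side accepts the mismatch but confines it.

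- **Wording leaves room.** The Introduction promises repeated death-registry searches without dates, and Section V gives the recruitment dates only as an example. Enrollment is also dated from the earliest qualifying measurement, so a patient measured on or before 30 November 1987 could reach five years. This is why the conclusion should read: none on the stated dates. It does not rescue the horizon. Sections VIII and IX list no later search, and the protocol describes no such early group.
- **Registry with a survival model.** The proportional hazards analysis uses all censored follow-up, and Table 1 claims no power at five years. Both points are true, and they limit the damage. The model still gives no observed mortality beyond the last follow-up.
- **Three-year mortality.** A reader might infer from the two-year search that this fails too and that Table 1's three-year column is too optimistic. The protocol does not support that for the main cohort, as Steps 3 and 4 show. Power at a two-year search is beside the point, because Table 1 claims power at three years.
- **Cardiovascular mortality.** A reader might infer that it cannot be obtained beyond one year, because the long-term search is described as vital status only. Section X names the death certificate as the source of cause of death and sets no time limit. What is undescribed is how certificates are retrieved for deaths found through the registries. That is an operational gap, not a contradiction.
- **Crude reporting.** A reader might fear that the project Year 3 and Year 5 searches would be reported as three- and five-year mortality. Nothing in the protocol proposes this.

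**Conclusion.** The concern holds for five-year mortality. On the stated recruitment and search dates, no patient in the nine-month cohort of about 6,000 can have an observed five-year status. Follow-up ends at 4.17 to 4.91 years at the latest, and earlier if the second search is run early in its window. The primary objective and subsidiary objective 1 therefore each name a horizon that the design cannot deliver.

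One- and three-year mortality are supported for the main cohort, and the three-year column of Table 1 stands. Rare-etiology patients recruited late are a separate gap: those enrolled after 30 November 1989 reach neither three nor five years.

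The result rests on the Section VIII dates, on enrollment dates falling within the recruitment window, and on no search beyond those listed. That the project-year labels were mistaken for years of follow-up is a plausible explanation, but the protocol does not say so.

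**What to change.** Choose one of two changes and make Sections II, VIII and IX (both Follow-up Data and Endpoint Data) agree.

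1. **Keep five years.** Date the last registry search so that it covers deaths through at least 30 September 1993. Five-year results then come about 10 months or more after the present end of the timetable. No patient contact is needed. If the project Year 5 search is moved, complete three-year results for the main cohort wait as well; if it is kept, the cost is one further registry match.
2. **Drop five years.** Replace five years by four years in the primary objective and subsidiary objective 1, and keep one and three years. Time the second search so that it covers deaths through 30 September 1992, which gives the last nine-month enrollee four full years and fits within project Year 5. The cost is the loss of the longest horizon. The objectives should not be cut to one, two and four years, since that would discard a three-year horizon the schedule supports.

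Under either option, limit the three-year and the longest-horizon objectives to the nine-month cohort, or state the shorter horizon that applies to late rare-etiology enrollees. Coverage through 30 September 1993 would still give a patient enrolled on 30 June 1991 only 823/365.25 = 2.25 years.

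A sentence in Section IX on obtaining certificates for registry-identified deaths would also help. It is a clarification and not part of the correction.

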#### Endpoint Data

The follow-up endpoints will provide two sets of information. The first set will be one-year information on vital and on major non-fatal cardiovascular events, including recurrent and/or new complications requiring hospitalization such as worsening of functional status, myocardial infarction, stroke, pulmonary complications, severe serious arrhythmias, drug toxicity, and cardiac surgery--including cardiac transplantation. The second set of endpoint data will provide long-term ascertainment of vital status, approximately two years and approximately four years after enrollment in the SOLVD Registry.

### X. STATISTICAL ANALYSIS

The primary outcome is all-cause mortality. Thus, the main variable for analysis will be the time from entry into the Registry until death. Cardiovascular mortality as well as other causes of death will be examined from major categories of the underlying cause of death from the death certificate. The analysis of the major outcome of death will involve the use of the proportional hazards model (Cox, 1972). This analysis will allow for the adjustment of baseline covariates thought to be of prognostic importance; for example, ejection fraction, age, sex, race, etiology. Similarly, analyses will be conducted for morbid events. A careful evaluation of the suitability of the proportional hazards assumption will be conducted as part of these analyses. In addition, the relationship of the echocardiographic and Holter variables to prognosis (collected systematically on the 1000 patients) will be assessed. The data will be analyzed separately in a number of subgroups based on etiology, sex, age, functional class, etc.

### Appendix A

### A1: SOLVD REGISTRY FLOW DIAGRAM

.4

			19
	SOLVD	REGISTR	
	BASEL	NE FORM	
	11/1	1/87	
REGISTRY ID:	FOR	i: R B F VERS	SION: A VISIT: 0
INSTRUCTIONS	This form is to be completed on all consecut using only the information available from the To be eligible for the Registry, the patient a diagnosis of congestive heart failure configuration Please print clearly when entering a response eral Instructions for Completing Forms for com-	a appropriate medical reco must either have an EF <= firmed by radiologic eviden te into the boxes. See the	rds. 45% or have hce.
	· •		
	SOLVD MAIN REGISTRY BASELINE FORM	(screen 1 of 15) (RBF pag	e 1 of 8)
A. IDENTIFY	ING INFORMATION	B. ELIGIBILITY ASSESSMEN	T Unrec
1.1 Today's	Date:/ // // /	
 
Most recently measur (should be 7 or more diac surgery, FTCA,
 
	ed Ejection Fraction days after an MI, car- or balloon valvuloplasty):
1.2 Initial	s of person completing form:	3.1 Percentage:	
2.1 Last Nam		3.2 Date://	Day / The Year
2.2 First N		3.3 Hethod utilized:	Radionuclide R Contrast angiography A 2-D echo E
2.3 Middle 1	Initial:		Not on chart U

2 (1.1. 1) (1.1. 1) (1.1. 1) (1.1. 1)

• .

•

				1			
	Yes	No l	Inrecorded	c.	DEMOGRAPHIC INFORMATION		
4.1	Primary diagnosis of heart failure and chest X-ray consistent with heart failure (X-ray should be 7 or			6.	Sex:	Male Female	M F
	more days after an MI, cardiac surgery, PTCA, or balloon valvuloplasty) Y	N	υ	7.	Ethnic Identity	American Indian	1
1. 9	Date of multiplan Y-news					Asian	2
4.4	Date of qualifying X-ray:					Black	3
	Month Day Year					Caucasian	4
53 1000				1		Hispanic	5
5.	Reasons for exclusion from Registry					Other	6
5.1	Presence of non-valvular congenital heart disease Y	N	U			Not on chart	7
5.2	Presence of any non-cardiac life- threatening disease which is unlikely to allow the patient to survive one year (Includes 11, 12, 13, 17, 18, 21 and 23 of SOLVD trials)	N	υ	8.	Date of Birth:	Year	
5.3	No telephone or reliable means of contact/follow up Y	N	υ	9.	Social Security Number (Ca (IMPORTANT!! MUST BE COMPL		):
5.4	Failure to consent to Registry Y	N	U		-	-	
5.5	Is patient eligible for Registry? Y (If NO, exit form)	N				Bagan antanan da na vindu na	-

SOLVD MAIN REGISTRY BASELINE FORM (screen 3 of 15) (RBF page 2 of 8)

10.1 Participant Street Address:	10.5 Zip Code/Canadian or European Postal Code:
	11. Participant Telephone Number (Home):
	HOSPITAL INFORMATION
10.2 City:	12.1 Hospital name:
10.3 State/Province:	12.2 Hospital street address:
10 4 Country:	

12.3 City:	14.2 First Name:
	15.1 Street address:
12.4 State/Province:	
12.5 Country:	
12.6 Zip Code/Canadian or European Postal Code:	15.2 City:
13. Patient hospital ID number:	
PRIVATE PHYSICIAN INFORMATION	15.3 State/Province:
14.1 Last Name:	15.4 Country:
	15.5 Zip Code/Canadian or European Postal Code:

4

SOLVD MAIN REGISTRY BASELINE FORM (screen 5 of 15) (RBF page 3 of 8)

•

16. Telephone Number (private physician):	19.1 Street address:
NEAREST RELATIVE OR FRIEND NOT RESIDING WITH PARTICIPANT	
17.1 Last name:	
	19.2 City:
17.2 First name:	
18. Relationship:	

(Nearest relative/friend continued)	D. X-RAY FINDINGS Ye	s
19.3 State/Province:	<pre>21.1 Is chest-X-ray available? Y    (If NO, skip to section E)</pre>	
19.4 Country:	21.2 Date of most recent chest X-ray (should be 7 or more days after MI, cardiac sur- gery, PTCA, or balloon valvuloplasty): ////// Month Day Year	
20. Telephone number:	21.3 Is this X-ray the qualifying X-ray? Y	
	22. Pulmonary congestion:	
	22.1 Evidence of pulmonary congestion Y (If NO, skip to Q. 23)	!
	22.2 Basal or perihilar vascular blurring	!
	22.3 Kerley B lines Y	!
	(continued)	

Т

SOLVD MAIN REGISTRY BASELINE FORM (screen 7 of 15) (RBF page 4 of 8)

	Y	es	No			Yes	No	Unreco
	Alveolar or pulmonary edema		N	24.	Indicate all of the following th rently (including etiology speci	at o fied	ccur abo	concur ve):
22.5	Pleural effusion	Y	N	24.1	Ischemic heart disease (IHD)	Y	N	U
E.	ETIOLOGY OF DISEASE	223		24.2	Hypertensive heart disease (HHD)	¥	N	U
23.1	What is the primary etiology of participa heart disease (choose only one of the fol	int's	ng):	24.3	Active myocarditis	Y	N	U
	Ischemic heart disease (IHD)		1	24.4	Idiopathic cardiomyopathy	¥	N	U
	Hypertensive heart disease (HHD)		2	24.5	Specific cardiomyopathy (ex: viral, toxic, ETOH, post-	Y	N	U
	Active syocarditis		3		partum, history of cocaine use) (If NO or UNRECORDED, skip to Q.	24.	7)	
	Valvular heart disease - aortic		4	24.6	Specify:			
	Valvular heart disease - mitral		5	24.7	Valvular heart disease - aortic	Y	N	U
	Idiopathic cardiomyopathy (specifics unknown)		6	24.8	Valvular heart disease - mitral	Y	N	U
	Specific cardiomyopathy (ex: viral, toxic, ETOH, postpartum, history of cocaine use) (If none, skip to Q. 24)		7					
23.2	Specify:		-		•			

-----

F. RELATIONSHIP TO SOLVD TRIALS (SKIP TO SEC G IF EF> 35%)		Yes	No	Unreca
	26.3 Complex congential heart disease	Y	N	U
trials, copy Eligibility ID:	26.4 Myocardial infarction within 30 days of expected randomization	Y	N	U
	26.5 History of intolerance to . enalapril	Y	N	U
25.2 If participant has been randomized into the SOLVD trials, copy Randomization ID:	26.6 Currently taking ACE inhibitor and unwilling/unable to discontinue	I Y	N	U
	26.7 Renal failure	Y	N	U
(If participant randomized, SKIP to Q. 27) Yes No Unrecorded	26.8 Uncontrolled hypertension	Y	N	U
	26.9 Cor Pulmonale	Y	N	U
26. If participant was considered for but excluded from the SOLVD trials, please	26.10 Advanced pulmonary disease	Y	N	υ
	26.11 Major neurological disease	Y	N	U
26.1 Hemodynamically significant valvular or outflow tract obstruction Y N U	26.12 Cerebrovascular disease	Y	N	U
26.2 Constrictive pericarditis Y N U	26.13 Collagen vascular disease	Y	N	U

Т

SOLVD MAIN REGISTRY BASELINE FORM (screen 9 of 15) (RBF page 5 of 8)

		Yes	No	Unrecorded		Yes	No	Unrec
26.14	Any major cardiac surgery likely	¥	N	U	at an evented electificant month			
26.15	Unstable angina pectoris	Y	N	U	26.23 Suspected significant renal artery stenosis	Y	N	U
26.16	Cancer	¥	N	U	26.24 Woman likely to bear children	Y	N	U
	Immunosuppressive therapy			U	26.25 Other investigational drug pro- tocols (except compassionate use)	Y	N	U
	Active myocarditis Significant primary liver			U	26.26 Failure to give consent for the SOLVD trials	Y	N	U
26.20	disease Likely to be nonadherent (alco-	Y	N	U	26.27 Lack of adherence or tolerance to medication	Y	N	U
	holism, drug addiction, lack of a fixed address, etc.)	¥	N	υ	26.28 Lack of adherence to placebo run-in	Y	N	U
26.21	Syncopal episodes presumed to be due to life-threatening arrhythmian	6 Y	N	υ				
26.22	Other life-threatening disease or not realistically expected							
	to be discharged alive	Y	N	U				

				1			20	
27. For which trial is/was the parts		nt be	ing			Yes	No	Unreco
				28.10	Peripheral vascular disease	Y	N	υ,
Prevention Treatment Not considered/randomized	1			28.11	Edema	¥	N	U
		•		28.12	Breathlessness on exertion	Y	N	U
G. CLINICAL HISTORY 28.1 Date history taken (within 3 month)			Unrecorded rollment)	28.13	Asthma (If NO or UNRECORDED, skip to Q		N 15)	U
Month Day Year			.*	28.14	Approximate duration of asthma (in years):			]
28.2 Diabetes mellitus	¥	N	U	28.15	Pulmonary edema	Y	N	U
28.3 Chron. obstructive pulm. dis	¥	N	U	29.1	Previous myocardial infarction? (If NO or UNRECORDED, skip to Q		N	U
28.4 Cerebrovascular accident	Y	N	υ		Enter date of most recent myoca			
28.5 Angina pectoris	¥	N	U	29.2	Enter date of most recent myoca	TUIAI		arce101
28.6 Peripheral embolism	Y	N	U		Month Year			
28.7 Pulmonary embolism	¥	N	U	29.3	Was the MI complicated by pulmo	narv	edem	۵.
28.8 Syncope	¥	N	U		shock, or heart failure?	Y	N	, n
28.9 Hypertension	Y	N	U					

SOLVD MAIN REGISTRY BASELINE FORM (screen 11 of 15) (RBF page 6 of 8)

٠

----

. .... . . .**...** 

30.	Smoking history	Yes	No	Unrecorded	Yes No Unreco
30.1	Has the participant ever been a smoker (tobacco)? (If NO or UNRECORDED, skip to Q.	¥ 31)	N	U	32. Permanent pacemaker? Y N U
30.2	Does the participant currently smoke?		N	U	33. Use of automatic implantable defibrillator? Y N U
31.	Alcohol consumption history	•	M	U I	34.1 Previous cardiac surgery, PTCA, or balloon valvuloplasty? Y N U (If NO or UNRECORDED, skip to Q. 35)
31.1	Has the participant ever regular consumed alcohol? (If NO, skip to Q. 32)		N	U	34.2 Enter date of most recent cardiac surgery, PTCA, or balloon valvuloplasty:
31.2	Is there history of alcohol abuse? (See Manual of Operations for guidelines)		N	υ	Month Year
31.3	Does the participant currently consume alcohol?	Y	N	υ	

ł

- -

	Type of cardiac surgery:	Yes	No	Unre	corded			2	les	No
34.3	Coronary artery bypass graft	¥	N	U	ſ		36.2	Potassium-sparing diuretic	Y	N
34.4	Valve replacement - aortic	¥	N	U	l			Antiarrhythmic drug other than bet blocker or calcium antagonist	ra- Y	N
34.5	Valve replacement - mitral	Y	N	U			36.4	Regular use of antiplatelet	Y	N
34.6	Percutaneous transluminal coronary angioplasty (PTCA)	Y	N	U	1		36.5	Beta-blocker	Y	N
34.7	Balloon walwuloplasty	Y	N	U	I		36.6	Long-acting oral nitrate or paste	Y	N
34.8	Other	Y	N	U	I		36.7	Hydralazine	Y	N
34.9	(If NO or UNKNOWN, skip to Q. 35 Specify:	·)			-		36.8	Open-label ACE inhibitor (Select "S" if in SOLVD trial)	Y	N
	EDICATIONS IN USE AT LAST HOSPITA	LI-		Yes	No		36.9	Digitalis	Y	N
	ATION OR OUT-PATIENT VISIT				••		36.10	Calcium antagonist	Y	N
35. I	Date of last hospitalization or ou	it-pat 7	ien	t vis	it:		36.11	Other vasodilator	Y	N
							36.12	Antihypertensive (other than above	e) Y	N
	Month Day Year						(conti	inued)		
36.1	Potassium-losing diuretic	Y	N							
	SOLVD MAIN REGISTRY BASELINE FORM (screen 13 of 15) (RBF page 7 of 8)									
		v.	-	No		T				

	Yes	No	
36.13	Other inotropic agent Y	м	39. Height (enter inches or cm):
36.14	Anticoagulant Y	N	39.1 in.
36.15	Insulin Y	N · .	
36.16	Steroids Y	N	39.2 cm.
36.17	Beta-2 agonist inhalers Y	N	beats/
36.18	Potassium supplements Y	N -	40. Heart rate: min
I.	PHYSICAL EXAMINATION (At admission if hosp if outpatient, last recording within 3 mon	italized; ths)	41. Systolic blood pressure: mm Hg
37.	Date of physical exam: ////// Month Day Year		42. Diastolic blood pressure:
38.	Weight (enter 1bs. or kg.):		43. Any of the following present? Yes No
